The anticipated flow of the study during the Intervention M study blocks is summarized in Figure 1. CRCs and research personnel will begin by setting up their home base of consents and platforms (video clips, printed materials, and scripts for messaging).

Figure 1: Intervention M Arm Study Flow

Introduction to ED Staff: Clinical Research Coordinators (CRCs) will set up their workstation in the ED and introduce themselves to ED staff (nurses, physicians, and mid-levels), informing them that they will be doing the PROBOOSTVAXED study that day. **They will avoid telling providers whether this is an intervention versus control arm.**

Initial Screening and Scripted Consent for Surveys: CRCs will review ED dashboards for inclusion and exclusion information. When an eligible patient is identified, the CRC will ask the nurse or doctor caring for the patient whether it is okay for them to approach the patient about the study. For provider approved patients: CRCs will approach eligible patients and deliver a scripted consent for two short surveys: the (Pre-intervention) Intake Survey and the (Post-Intervention) Vaccine Acceptance Survey. See Scripted Consent for the Intervention M period.

They will also get written HIPAA authorization for review of their ED EHR. If the patient does not agree to this HIPAA review of their EHR, they will be excluded from the study. Participants will not be compensated for participation.

CRCs will complete screening and enrollment log indicating whether they agreed to participate. If they agreed to participate, the CRC will assign a Study ID#.

Intake Survey: We will administer the INTAKE SURVEY to participants. CRCs will have the option of inputting surveys to REDCap on iPads in real time or using paper surveys (and later inputting into REDCap). These surveys are to be delivered orally (CRC asks questions), not via handing them out. The Intake Surveys are the same for all three arms of the study.

Intervention M (messaging): The intervention will consist of three messaging platforms that were developed specifically to reduce booster vaccine hesitancy. All platforms have been reviewed by the UCSF Committee on Human Research.

- 1) Video clips short (approximately 3-minute) Public Service Announcement type videos to be viewed by participant using a QR code on their smartphone. If no smartphone is available, the video will be shown to the participant on an iPad.

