- 2) Printed materials one page information sheets handed to subjects by CRCs.
- 3) Face to face messaging short (< 1 minute), scripted message from the patient's providers in the ED (nurse or provider)

Each site will maintain a library of

A. 5 versions of the videos – the version used in any participant will be tailored to that participant's stated race/ethnicity. See *** below

B. 5 versions of printed flyers – likewise, the version will be tailored to the participant's stated race/ethnicity. See *** below

C. 1 version of scripted message to be delivered in English or Spanish.

COVID-19 Booster Vaccine Flyer, Videos, and Telling Provider to Deliver Message: Interventions will be delivered in real-time patient visits in site EDs. during waiting times such

Interventions will be delivered in real-time patient visits in site EDs, during waiting times such that they will not interfere with patient care. At the end of the survey, the CRC will deliver the booster vaccine information flyer and ask the patient if they will watch a short video about booster vaccines. If they agree to watch the video, the CRC will give them a QR code to view the video on their smartphone. If they do not have a smartphone, they will show them video on an iPad. After finishing with the video, the CRC will tell the subject that they will be back in about an hour for the Vaccine Acceptance survey. The CRC will then leave the room and ask the patient's primary provider (doctor, mid-level practitioner, or nurse) to deliver the booster vaccine message (hand them the scripted message). This message is short and should not significantly impact provider workflow. Notably, vaccine messaging is recommended in the ED by the American College of Emergency Physicians and other health care organizations (Centers for Disease Control).

***We will deliver messaging from our platform libraries in patients' preferred language (English, Spanish). To the extent possible, we will follow recommendations to choose platforms from site libraries that match video clip and printed material messengers with subjects' likely preferences for race, ethnicity, age, and gender (e.g., Latinx messenger on video clip with Latinx participant).

Vaccine Acceptance Survey (Post-Intervention) in the ED: We will administer the Vaccine Acceptance Survey: INTERVENTION GROUP at some time (generally 30 minutes but up to 3 hours) after the Intake Survey.

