Primary and Other Outcome Ascertainment: Primary outcome for Specific Aim I is booster vaccine uptake (at any vaccination location) within 30 days after participants' index ED visit, comparing the Intervention M arm versus the Control arm. For ascertainment of this outcome, we will:

- 1) Review the EHR the day after participants' index visit (as described for the secondary outcome ascertainment below).
- 2) Review the EHR at 30 days for receipt of a booster vaccine.

3) Conduct follow-up phone calls (*Have you received a booster vaccine since your emergency department visit?*) 30 days after index ED visits for those who did not get the vaccine in the ED and who consented to follow up.

Secondary outcome (vaccination in the ED) ascertainment will occur by review of each participant's ED EHR by research staff on the next workday after their index ED visit. Staff will check the EHR to confirm receipt (or non-receipt) of a booster vaccine in the ED. This review will be conducted in a blinded fashion – the research staff person reviewing the EHR will be unaware of participant's study group assignment.

Participants who have confirmed receipt by EHR review will be deemed "vaccinated in the ED". Conversely, participants who do not have confirmed receipt by review will be deemed to be "not vaccinated in the ED".

Outcome and Ascertainment of Specific Aim II

Our outcome for Specific Aim II is booster vaccine acceptance (defined as a response of "yes" to the question, "Would you accept the booster vaccine in the emergency department today if your doctor asked you?"), comparing the Intervention M arm versus Intervention Q arm. This outcome will be ascertained during the Vaccine Acceptance Survey in both arms.

Outcomes and Ascertainment of Specific Aim III

Our outcome for Specific Aim III is 30-day booster vaccine uptake (at any vaccination location), **comparing the** Intervention Q arm (Vaccine Acceptance Question, No Messaging) versus the Control arm (No Messaging, No Vaccine Acceptance Question). This outcome will be ascertained in the same manner as the primary outcome of Specific Aim I.

A secondary outcome for Specific Aim III is booster vaccination in the ED, comparing the Intervention Q arm versus the Control arm. This outcome will be ascertained in the same manner as the secondary outcome of Specific Aim I.

30-Day Phone and EHR Follow Up

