The outcome is booster vaccine acceptance (defined as a response of "yes" to the question "Would you accept the booster vaccine in the emergency department today if your doctor asked you?"). This outcome will be compared using mixed logistic regression with a fixed effect for randomization assignment, a normally distributed random effect to allow for clustering by enrolling center, and restricted cubic splines to allow for secular trends during the study period. The treatment effects will be tested by the coefficient for the fixed effect of study arm along with 95% confidence intervals.

Analysis for Specific Aim III

For Specific Aim III, the outcome is uptake (receipt) of a booster vaccine at any vaccination location within 30 days of the index ED visit. We will compare outcomes in participants seen on Intervention Q arm dates with those seen on Control dates to test our study hypothesis: Implementation of an ED protocol in which patients are asked whether they will accept a booster vaccine (and notifying ED providers when they say they will accept it) will be associated with increased booster vaccine uptake in vaccinated ED patients.

A secondary outcome for Specific Aim III is receipt of a booster vaccine during the index ED visit, comparing participants seen on Intervention Q dates with those seen on Control dates - ascertained by check of the participant's EHR on the day after their ED visit.

Subgroup Analyses

Another focus of this research is on ED patients who lack primary care group, defined on the Intake survey question: "Do you have a regular clinic or doctor for medical care?" We will analyze outcomes according to the binary indicator of having primary care – yes versus no (and unsure).

We will additionally stratify outcomes by study site (representing different regions of the country and different communities), vaccine administration capability, age, gender, primary language, and race/ethnicity.

Subgroups will be tested by adding a subgroup by intervention interaction to the mixed logistic regression. A subgroup will be considered significant if the pairwise intervention by subgroup omnibus test is significant at the 0.05 level.

Rationale for time (1-day unit) cluster and consideration of Alternative Study Designs:

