The sample size calculations for this research are governed by hypothesis testing of Specific Aim I -- Implementation of booster messaging platforms will be associated with increased booster vaccine uptake (primary outcome) in unvaccinated ED patients. Considering the high benefit of increasing vaccine uptake and the negligible risk of the intervention (a trusted messaging program), even a small effect size of increased uptake would be a clinically important difference. By investigator consensus, we have determined that the intervention would be clinically useful if it increased booster vaccine uptake by 7%.

We base the sample size calculation on the comparison of the proportion of patients who accept the vaccine between the Intervention M and Control time periods using standard formulae for individual randomization. We have verified that these sample sizes are conservative by simulation of data using a mixed random effects model. Our baseline level of vaccine uptake in the control arm is estimated to be approximately 5%. With this uptake level we find that at an alpha=0.05 level and a power of at least 0.80, we will need to enroll 744 participants (248 in each arm) in the study to detect the difference of interest (a setting in which the vaccine uptake rate will increase by 7% during Intervention periods vs Control periods).

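### Aim II acceptance is, as the procedures imply, told to an arm-aware coordinator who in arm M also gave the messaging, so M versus Q can be biased towards the hypothesis by an unknown amount.

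*Combined protocol and SAP*

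**What the plan says.** **Outcome.** Section XIII defines Aim II's outcome as a yes to a single question: would the participant accept the booster in the ED today if their doctor asked? It compares M with Q and adds: "This outcome will be ascertained during the Vaccine Acceptance Survey in both arms".

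**Mode.** The Intake Survey paragraph of Section IX states: "These surveys are to be delivered orally (CRC asks questions), not via handing them out". It also says that "CRCs will have the option of inputting surveys to REDCap on iPads in real time or using paper surveys". The paragraphs on the Vaccine Acceptance Survey do not restate the mode. Section XIV has CRCs recording survey responses, and Section XI describes what follows when a participant says they will accept.

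**Who asks.** Under Section V, sites uncover the day's assignment that morning, so the CRC knows the arm. In M, the CRC gives the flyer, offers the video, and then "the CRC will tell the subject that they will be back in about an hour for the Vaccine Acceptance survey". The survey is placed generally 30 minutes, and up to 3 hours, after intake. The ED provider, not the CRC, is asked to give the scripted face-to-face message.

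**Arm Q.** The workflow is that of M without the messaging, and the key outcome questions are the same.

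**Blinding.** Sections IX and XIII specify blinded record review. Section XIII gives the 30-day follow-up to a different CRC from the one who recruited that day. Neither section says anything equivalent for the acceptance answer.

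**The concern.** Acceptance is the most subjective primary outcome in the plan and the only one without a blinded assessor. Participants in M are asked by someone who has handed them promotional material and offered them a video. Some may say yes partly to please that person. In Q, the person asking has promoted nothing. A reporting difference of this kind would add to the M minus Q contrast in the direction of the hypothesis.

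The analysis cannot separate the two effects. The Section XV model for Aim II contains study arm, a random centre effect and splines for calendar time. A reporting effect tied to arm falls entirely into the arm coefficient. At stake is whether a positive Aim II result shows that messaging changed willingness, or partly that it changed what people told the messenger.

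**Working it through.** **1. The plan's own figure.** Section XVII sizes Aim I only: "Our baseline level of vaccine uptake in the control arm is estimated to be approximately 5"%, a useful increase of 7 points ("the intervention would be clinically useful if it increased booster vaccine uptake by 7"%), and "we find that at an alpha=0.05 level and a power of at least 0.80, we will need to enroll 744 participants", which is 248 per arm. Sidedness is not stated; I take it as two-sided, in line with the 95% intervals ("The treatment effects will be tested by the coefficient for the fixed effect of study arm along with 95% confidence intervals"). With pooled variance and no continuity correction, and mean rate (0.05 + 0.12)/2 = 0.085:

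n = [1.960·√(2 × 0.085 × 0.915) + 0.842·√(0.05 × 0.95 + 0.12 × 0.88)]² / 0.07² = 248 per arm; 3 × 248 = 744.

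This matches, with power 0.800. The present point does not affect it. I use it only for the arm size.

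**2. Inputs for Aim II.**
- Arm size: 248 each in M and Q (Section XVII).
- Acceptance without messaging: no planning value is given. The overview's earlier survey found 57% of non-boosted participants hesitant, so 100% − 57% = 43% acceptance. That population is not identical to this trial's, so I use 43% to 50%.
- Net reporting differential b, M minus Q: not in the documents. I assume 0, 3, 5 and 8 points.
- True messaging effect: zero, to isolate the false-positive rate.

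**3. Standard error of the difference.** SE = √(2p(1 − p)/248).
- p = 0.43: √(2 × 0.43 × 0.57/248) = 0.0445.
- p = 0.50: √(2 × 0.50 × 0.50/248) = 0.0449.

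**4. Two-sided false-positive rate.** Rate = Φ(b/SE − 1.96) + Φ(−b/SE − 1.96).

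| Net differential b | p = 0.43 | p = 0.50 |
|---|---|---|
| 0 | 0.050 | 0.050 |
| 0.03 | 0.104 | 0.103 |
| 0.05 | 0.203 | 0.200 |
| 0.08 | 0.436 | 0.429 |

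That is about 10%, 20% and 43%. This is a simple two-proportion approximation; it ignores the centre effect and the time splines.

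**5. Courtesy in both arms.** Suppose true acceptance is 43% in both arms and a fraction f of the other 57% say yes out of courtesy. The bias is (f_M − f_Q) × 0.57.
- 10% in both: 0.
- 10% in M, 5% in Q: 0.05 × 0.57 = 2.85 points. The probability of a significant result favouring M is 0.093.
- 15% in M, 5% in Q: 0.10 × 0.57 = 5.7 points; probability 0.245.

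The last two probabilities are for the M-favouring direction only, where the nominal value is 0.025. Only the difference between arms matters.

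**The case against.** A reader might infer that interviewer and courtesy effects operate in M alone, and that they do inflate the result. The documents support neither. Q has the same workflow, a CRC who equally knows the arm, and the same key questions. General effects of being asked by study staff therefore arise in both arms and largely cancel, as step 5 shows. Nothing in the documents shows that the M-specific part is present or how large it is.

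Other points also count:
- The outcome question has fixed wording, which leaves little room for probing, and it refers to the doctor's request rather than the CRC's.
- Standard training and scripts are planned.
- Participants may refuse the flyer or video, the survey comes some time after them, and the face-to-face message is the provider's task.
- The oral-mode sentence stands in the Intake Survey paragraph, so applying it to the acceptance survey is an inference, though Sections XI and XIV point the same way.
- Aims I and III rest on 30-day uptake with blinded follow-up, and M versus Q on that outcome is a planned secondary comparison.

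All of this narrows the point. It does not remove the one feature that differs by design: in M, the person who gave the messaging takes the answer. The uptake comparison is only a partial check. It measures a different outcome, and only some sites can vaccinate in the ED.

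**Conclusion.** The point holds as a risk of differential reporting bias confined to Aim II. Its plausible direction favours the hypothesis, and its size is unknown. If the net differential is zero there is no bias. If it were 3, 5 or 8 points, the two-sided false-positive rate would be about 10%, 20% or 43% instead of 5%. Those rates assume 248 per arm, 43% to 50% acceptance and no true messaging effect; the differentials are illustrations, not estimates. They also assume that the acceptance question is answered orally, as the procedures imply. The planned model cannot correct the bias afterwards, so it is best reduced at data collection. The sample size and the primary outcome of Aims I and III are unaffected.

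**What to change.** In both M and Q, have the CRC read the final acceptance question aloud in its fixed wording, and let the participant mark yes, no or unsure privately on the iPad or paper form already in use. At vaccine-capable sites, put a tick-box on the same form giving permission to notify the ED provider, so that the notification step in Section XI does not require the participant to repeat the answer aloud. The CRC opens the form only after it is submitted. Allow a spoken answer only when the participant cannot mark the form. Record the answering mode and tabulate it by arm.

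In the report, state the remaining limitation and present Aim II beside the M versus Q comparison of 30-day uptake.

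**Cost.** A short change to the procedures, a field for answering mode, a permission tick-box, brief staff retraining and a few extra seconds per participant. No added staff, devices or participants are needed. Some participants will still answer aloud. The bias is reduced rather than removed, because the same CRC still reads the question, and at vaccine-capable sites must still act on a yes.

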We will enact rigorous methods for clinical trial quality assurance and performance improvement, including: 1) systematic review of enrollment logs, 2) weekly audits of random samples of data for accuracy and missing elements, and 3) structured review of protocol deviations or violations. The Central Study Coordinator will prepare monthly summary report cards, tabulating individual site quality assurance metrics for review during scheduled Steering Committee calls. The overall study PI ([name]) will discuss site-specific data with site PIs individually and summarize these data collectively during Steering Committee calls, with prompt dissemination of plans for process improvement.

VIII. Recruitment, Inclusions, Exclusions, and Consent

Practical budget considerations and limits on research personnel in patient care areas during the COVID-19 pandemic, preclude 24/7 delivery of the PROBOOSTVAXED trusted messaging platforms and enrollment in this study. We will use a convenience sample technique to approach all eligible adult patients who present to our study EDs during 8-hour (one-day) blocks, typically beginning at approximately 9 a.m. and continuing to approximately 5 pm. Sites will be given leeway to vary their particular study time hours, as long as these study hours remain consistent from week to week.

Inclusions will be:

- 1) Age > 18 years
- 2) Presenting to ED
- 3) No receipt of COVID-19 booster within prior 6 months
- 4) Able to provide informed consent
- 5) Fluent in English or Spanish

6) Anticipated ability to complete study intervention in ED i.e., able to watch a 3-minute videoclip

Reviewing ED triage information, we will exclude patients with the following characteristics:

- 1) Major trauma such that it will preclude survey
- Inability to participate in a survey because of intoxication, altered mental status, or critical illness
- 3) Incarceration
- 4) Psychiatric hold
- 5) Patients who state that they have already received a bivalent COVID-19 booster vaccine or other COVID-19 vaccine within the prior 6 months
- 6) Patients who are in the ED for suspected acute COVID-19

[figure not shown]
NOTE: For all three study arms, study procedures should be performed in patient waiting times and not interfere or disrupt patient care in any way.

IX. Study Procedures: Intervention Blocks

Procedures and workflow during PROBOOSTVAXED Intervention M Study Arm

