Primary and Other Outcome Ascertainment: Primary outcome ascertainment of 30-day uptake of booster vaccine will occur in three ways:

- 1) Ascertainment of vaccination in the ED by direct questioning and review of EHR records.
- 2) Blinded review of EHR at 30-days
- 3) For participants who have not received a booster vaccine upon questioning in the ED, staff will ask whether they will agree to phone follow-up at 30 days. For those agreeing to follow-up, we will obtain written consent for phone follow-up (phone follow-up consent form). We will then ask participants for their best phone number(s) to reach them for a follow-up phone call. Sites will maintain a separate password protected database of subject IDs and follow-up phone numbers.

This method will assure that all study participants, even those who refuse phone follow-up, will have at least two ways of study outcome ascertainment (1 and 2 above).

[figure not shown]
Secondary outcome ascertainment of booster vaccination in the ED will occur in two ways:

- 1) Direct questioning of participants and their providers in the ED: Research staff will ask participants and their ED providers whether the participant received a booster vaccine in the ED one hour but up to 6-hours after the Vaccine Acceptance Survey. Notably, ED patient visits are variable such that not all patients have stays lasting greater than an hour and a half. Research staff should endeavor to complete this ascertainment prior to discharge, even if that ascertainment occurs before an hour after the Vaccine Acceptance survey.
- 2) Review of each participant's ED EHR by research staff on the next workday after their index ED visit to confirm receipt (or non-receipt) of a booster vaccine in the ED. **This EHR review will be conducted in a blinded fashion the research staff person reviewing the EHR will be unaware of participant's study group assignment.**

Procedures and workflow during PROBOOSTVAXED Intervention Q Study Arm

The workflow during this arm is identical to the Intervention M Arm except there will be no messaging platforms delivered. The anticipated flow of the study during **Intervention Q Blocks** is summarized in Figure 2.

Figure 2: Intervention Q Arm Study Flow

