Introduction to ED Staff: Clinical Research Coordinators (CRCs) will set up their workstation in the ED and introduce themselves to ED staff (nurses, physicians, and mid-levels), informing them that they will be doing the PROBOOSTVAXED study that day. **They will avoid telling providers whether this is an intervention versus control arm.**

Initial Screening and Scripted Consent for Surveys: CRCs will review ED dashboards for inclusion and exclusion information. When an eligible patient is identified, the CRC will ask the nurse or doctor caring for the patient whether it is okay for them to approach the patient about the study. For provider approved patients: CRCs will approach eligible patients and deliver a scripted consent for two short surveys: the (Pre-intervention) Intake Survey and the (Post-Intervention) Vaccine Acceptance Survey. See Scripted Consent for the No Messaging arm period.

CRCs will complete screening and enrollment log indicating whether they agreed to participate. If they agreed to participate, the CRC will assign a Study ID#.

Intake Survey: We will administer the INTAKE SURVEY to participants. CRCs will have the option of inputting surveys to REDCap on iPads in real time or using paper surveys (and later inputting into REDCap). These surveys are to be delivered orally (CRC asks questions), not via handing them out. The Intake Surveys are the same for all three arms of the study.

[figure not shown]
Vaccine Acceptance Survey: We will administer the Vaccine Acceptance Survey at some time (generally 30 minutes but up to 3 hours) after the Intake Survey. The surveys in the control group retain the same key primary and secondary outcome questions as in the intervention group Vaccine Acceptance surveys. See Vaccine Acceptance Survey: No Messaging arm.

Primary and Other Outcome Ascertainment: Ascertainment of primary and secondary outcomes will occur in the same manner as in the Intervention M arm.

X. Study Procedures: Control Blocks

The workflow during this arm is identical to the Intervention Q arm except there will be no Vaccine Acceptance Question survey. The anticipated flow of the study during control blocks is summarized in Figure 3.

Figure 3: Control Arm Study Flow

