Introduction to ED Staff: Clinical Research Coordinators (CRCs) will set up their workstation in the ED and introduce themselves to ED staff (nurses, physicians, and mid-levels), informing them that they will be doing the PROBOOSTVAXED study that day. **They will avoid telling providers whether this is an intervention versus control arm.**

Initial Screening and Scripted Consent for Surveys: CRCs will review ED dashboards for inclusion and exclusion information. When an eligible patient is identified, the CRC will ask the nurse or doctor caring for the patient whether it is okay for them to approach the patient about the study. For provider approved patients: CRCs will approach eligible patients and deliver a scripted consent for two short surveys – the Intake Survey and the (Post-Intervention) Vaccine Acceptance Survey. See Scripted Consent for the No Messaging arm period.

CRCs will complete screening and enrollment log indicating whether or not they agreed to participate. If they agreed to participate, the CRC will assign a Study ID#.

Intake Survey: We will administer the INTAKE SURVEY to participants. CRCs will have the option of inputting surveys to REDCap on iPads in real time or using paper surveys (and later inputting into REDCap). These surveys are to be delivered orally (CRC asks questions), not via handing them out. The Intake Surveys are the same for all three arms of the study.

Primary and Other Outcome Ascertainment: Ascertainment of primary and secondary outcomes will occur in the same manner as in the intervention arms.

XI. Research Staff Informing ED Providers When Participants Will Accept COVID-19 Booster Vaccine for Intervention M and Intervention Q Arms

Only some study site EDs will have the capability of administering COVID-19 booster vaccines during the initial ED visit. The last question in the Vaccine Acceptance Survey **in both the Intervention M and Intervention Q arms** of the study is "Would you accept the COVID-19 booster vaccine in the emergency department today if your doctor asked you?" For study site EDs capable of administering the COVID-19 vaccine, when a participant says they will accept the vaccine, the CRC or research staff will ask the participant if it is okay to notify that participant's ED provider(s) – nurse and/or physician that they said they will accept the vaccine

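### Control has no defined start for the in-ED questioning that gates phone-follow-up consent, and Sections IX and XIII differ on what counts as uptake; take phone consent at enrolment in all arms and let blinded EHR review alone define ED vaccination

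*Combined protocol and SAP*

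**What the plan says.** **Timing.** Section IX (Intervention M, secondary outcome ascertainment) has staff ask about booster receipt "in the ED one hour but up to 6-hours after the Vaccine Acceptance Survey". That survey is itself given "generally 30 minutes but up to 3 hours" after the Intake Survey. Because "not all patients have stays lasting greater than an hour and a half", staff are told to try to finish before discharge, even if that means asking sooner. Section X describes the Control workflow as "identical to the Intervention Q arm except there will be no Vaccine Acceptance Question survey", and then states: "Ascertainment of primary and secondary outcomes will occur in the same manner as in the intervention arms".

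**Phone consent.** Section IX (Primary and Other Outcome Ascertainment) says: "For participants who have not received a booster vaccine upon questioning in the ED, staff will ask whether they will agree to phone follow-up". Those who agree then give written consent. Section XII requires this consent separately but gives no time for it. The 30-day follow-up part of Section XIII allows calls only to participants with written consent.

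**Source.** The first item in Section IX's list for the 30-day outcome is: "Ascertainment of vaccination in the ED by direct questioning and review of EHR records". Its list for ED vaccination likewise has two routes, questioning and next-workday EHR review. Section XIII lists two EHR reviews and the call for the 30-day outcome, and classifies ED vaccination by blinded EHR review only.

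**Control consent.** The consent paragraph in Section X names both the Intake Survey and the Vaccine Acceptance Survey, and refers to the same no-messaging script as Intervention Q.

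**The concern.** The primary outcome counts boosters received at any location, and Section XI says only some study EDs can vaccinate. Apart from the EHR, the phone call is the only source at 30 days. If the chance of being asked for phone consent depends on arm procedures, boosters can be counted unequally in Intervention M and Control (Aim I) and in Intervention Q and Control (Aim III). Aim II is not affected, because its outcome is the survey answer itself.

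Section XIII has EHR review and calls done by staff blinded to arm. No such protection is stated for the in-ED question, yet Section IX lets it serve as an outcome source and decide who is asked for phone consent. Separately, the Control consent paragraph as written describes a survey that Control participants do not receive.

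**Working it through.** The check is mainly a comparison of passages; the arithmetic only shows what can be said about size.

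1. **Start of questioning.** In M and Q the sequence is Intake Survey, acceptance survey, receipt question. In Control the middle step is removed and no other starting event is given. The before-discharge instruction sets an end point for all arms, but not a start for Control. Figure 3 (Control flow) is not shown.

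2. **Who can be called.** A call needs written consent (Section XIII), and consent is sought from those unvaccinated on in-ED questioning (Section IX). The only receipt questioning described is the one timed from the acceptance survey. On that reading, access to the call is settled during the ED visit and after the intervention in M and Q, and at no stated time in Control. A participant who leaves before being questioned is never asked.

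3. **A participant who reports an ED dose that is not in the EHR.**
   - Section IX: direct questioning is a listed source, so the participant could count as vaccinated for both uptake outcomes.
   - Section XIII: not vaccinated in the ED. With no EHR record at 30 days, the follow-up procedure leads to a call.
   - Section IX again: having answered yes, this participant was never asked for the consent that the call requires. The scripted call question also asks only about the time since the visit, so a dose given during it may be missed.

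4. **The log.** Section XIV records study arm and yes or no to follow-up calls. It has no entry for a participant who was never asked.

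5. **The plan's own figure.** Inputs from Section XVII: 5% in Control, a 7-point increase to 12%, alpha 0.05 (taken as two-sided), power 0.80. With pooled variance under the null, n per arm = [1.960 × √(2 × 0.085 × 0.915) + 0.842 × √(0.05 × 0.95 + 0.12 × 0.88)]² / 0.07² = (0.773 + 0.329)² / 0.0049 ≈ 248, or 744 in three arms. It reproduces exactly, and this point does not dispute it.

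6. **Size.** Let p be true 30-day uptake, s the share of boosters visible only by phone (taken as equal across arms), and r the share of those that the phone route finds in an arm. Observed uptake is p × (1 − s + s × r). With equal true uptake in M and Control, the observed difference is p × s × (r in M − r in Control). The documents supply p (5% in Control, 12% targeted in M) but neither s nor r. Since s and r can each lie anywhere from 0 to 1, the formula limits the loss only to between 0 and p: 0 to 5 points in Control, 0 to 12 in M. That range is too wide to inform. The sign depends on which arm has the lower r. If r is equal across arms, the spurious difference is zero whatever s is, which is why the remedy aims at equal access to the call.

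**The case against.** **Staff can work with the text.** They are told to question before discharge, even early, and Control staff can do that too. This stands: the timing is undefined for Control, not impossible to carry out.

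**Every participant has other routes.** Section IX says that even those who refuse calls have two means of ascertainment, and the follow-up procedure looks for any EHR record and notes where the dose was given. The EHR may therefore show outside doses. This stands, and it means that s could be small. It does not make access to the call equal across arms.

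**Unseen material may settle part of this.** Figure 3 might give a Control time point, and the script might already omit the acceptance survey. Neither would reconcile Sections IX and XIII on the outcome source.

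**Part of the remedy exists.** Section XIII already makes EHR review decisive for ED vaccination, and Section XIV already logs agreement to calls. What remains is to bring Section IX into line and to add an entry for those not asked.

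**A stronger reading to avoid.** A reader might add the two intervals (0.5 + 1 = 1.5 h to 3 + 6 = 9 h after the Intake Survey), set them against an 8-hour block "typically beginning at approximately 9 a.m. and continuing to approximately 5 pm", and infer that everyone enrolled in the last 1.5 h, 1.5/8 or about 19%, misses the phone request. The documents do not support that. The phone request and the timed question stand in separate lists, the half hour is a usual interval and not a minimum, early asking is allowed, and the block governs when patients are approached, not when consent must end. Nor do the documents say that the recruiter makes the phone request; they say only that staff do.

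**Conclusion.** The point holds as a defect of specification. The start of in-ED questioning is undefined for Control. Phone consent is sought after the intervention in M and Q and at no stated time in Control. Sections IX and XIII classify an uncharted ED dose differently. These follow from the text, with one assumption: that the questioning which triggers the phone request is the receipt questioning described in Section IX.

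Arm-dependent ascertainment for Aims I and III is a possibility, not a finding. A reader might infer a bias towards the intervention; the documents give no phone-consent rate, no share of boosters seen only by phone and no coverage by arm, so neither size nor direction is established. The Control consent sentence may be a drafting carry-over. The changes should be made because they are inexpensive and close a route to unequal counting of the primary outcome, not because a bias of known size has been shown. The sample size stays at 744.

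**What to change.** 1. Take written phone-follow-up consent at enrolment, before any intervention, in all three arms. Written HIPAA authorization is already placed at that step for Intervention M.
2. Align Section IX with Section XIII: blinded next-workday EHR review alone defines ED vaccination, and the in-ED answer determines neither uptake outcome. Word the 30-day call to cover a dose 'during or since' the visit, so that an ED dose missing from the EHR can still count for the primary outcome.
3. If in-ED questioning is kept, time it in all arms from the Intake Survey, which all arms share.
4. Remove the Vaccine Acceptance Survey from the Control consent wording, or confirm that the script already omits it.
5. Add 'not asked' to the Section XIV log, and report asked, agreed and reached by arm.

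**Cost.** Changes of wording in the protocol, consent script and call form, and one log entry. Enrolment takes slightly longer, and some participants later vaccinated in the ED will have given a consent that was not needed. An uncharted ED dose will not count for the secondary outcome, as Section XIII already implies. The follow-up request comes earlier in the visit in every arm. The current plan already makes that request later, but the earlier prompt could slightly narrow the Aim III contrast. Neutral wording, such as 'follow-up about your health care', limits this.
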